5.4.1.1. Dose Modifications

Dose modification guidance for AEs that have been previously observed in subjects receiving INCB050465 or are potential class-effect AEs are provided (see Table 3 and Table 5). The starting dose and dose reduction levels of INCB050465 are provided (see Table 4). Individual decisions regarding dose interruption and reduction should be made using clinical judgment and in consultation with the sponsor's medical monitor, taking into account relatedness of the AE to the study treatment and the subject's underlying condition. Adverse events that have a clear alternative explanation or transient (≤ 72 hours) abnormal laboratory values without associated clinically significant signs or symptoms may be exempt from dose-reduction guidelines.

Table 3: Guidelines for Interruption and Restarting INCB050465

ADVERSE EVENT	ACTION TAKEN
Chemistry	

 AST and/or ALT is Grade 3 ($> 5.0 \times \text{ULN}$). Note: In subjects with liver metastasis-related elevations at baseline, contact sponsor to discuss clinical management and possible dose reductions.	
Step 1: Interrupt INCB050465 and monitor weekly until the toxicity has resolved to \leq Grade 1.
 
Step 2: Restart INCB050465 at next lower dose with medical monitor approval. Monitor as clinically indicated.

Hematology	

 Grade 3 ANC ($< 1.0 \times 10^9/\text{L}$). Platelet count is Grade 2 (50 to $< 75 \times 10^9/\text{L}$) for subjects who enrolled with platelets $> 100 \times 10^9/\text{L}$. Platelet count is Grade 3 ($< 50 \times 10^9/\text{L}$) for subjects who enrolled with platelets $\leq 100 \times 10^9/\text{L}$. 	
Step 1: Interrupt INCB050465 up to 14 days until the toxicity has resolved to \leq Grade 1 or pretherapy baseline. For Grade 3 ANC, monitor at least weekly.
 
Step 2: Restart INCB050465 at same dose; monitor as clinically indicated.

 Grade 4 ANC ($< 0.5 \times 10^9/\text{L}$). Grade 3 or Grade 4 febrile neutropenia. Platelet count is Grade 4 ($< 25 \times 10^9/\text{L}$). 	
Step 1: Interrupt INCB050465 up to 14 days until the toxicity has resolved \leq Grade 2. (Monitor ANC at least weekly.)
 
Step 2: Restart INCB050465 at same dose. Monitor as clinically indicated. If recurs, start at next lower dose.

Table 3: Guidelines for Interruption and Restarting INCB050465 (Continued)

ADVERSE EVENT	ACTION TAKEN
Other toxicities	

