• Diarrhea/colitis.	See Table 5 .
• Pneumonitis (Grade 1)	Step 1: Interrupt INCB050465 until the toxicity has resolved. Step 2: Restart INCB050465 at next lower dose. Monitor as clinically indicated.
• Pneumonitis (Grade \geq 2)	Permanently discontinue INCB050465.
• Skin toxicity (eg, rash, pruritus, etc, unless otherwise specified) (Grade 2-3)	Step 1: Interrupt INCB050465 until the toxicity has resolved to \leq Grade 1. Step 2: Restart INCB050465 at same dose. If assessed as related to INCB050465, restart at next lower dose.
• Exfoliative dermatitis (Grade 1)	Step 1: Interrupt INCB050465 until the toxicity has resolved. Step 2: Restart INCB050465 at next lower dose. Monitor as clinically indicated.
• Exfoliative dermatitis (\geq Grade 2)	Permanently discontinue INCB050465.
• Intestinal perforation (any grade)	Permanently discontinue INCB050465.
• Pneumocystis jiroveci pneumonia infection	Interrupt INCB050465. Permanently discontinue INCB050465 if Pneumocystis jiroveci pneumonia infection is confirmed.
• CMV infection	Subjects with CMV viremia without associated clinical signs of CMV infection should be carefully monitored. Consider interrupting INCB050465 for subjects with CMV viremia and clinical signs of infection until the infection has resolved. Restart INCB050465 reduced by 1 dose level if approved by the medical monitor.
• Varicella zoster infection	Interrupt INCB050465. Restart INCB050465 only by approval of the medical monitor.
• Any Grade 1 or Grade 2 toxicity unless otherwise specified.	Continue INCB050465 and treat the toxicity; monitor as clinically indicated.
• Any Grade 3 toxicity, if clinically significant and not manageable by supportive care unless otherwise specified.	Step 1: Interrupt INCB050465 up to 14 days until the toxicity has resolved to \leq Grade 1. Step 2: Restart INCB050465 at same dose. If assessed as related to INCB050465, restart at next lower dose. If interrupted for > 14 days, contact the medical monitor for approval to restart INCB050465. Monitor as clinically indicated.
• Any recurrent Grade 3 toxicity after 2 dose reductions.	Discontinue INCB050465 administration and follow-up per Protocol. Exceptions require approval of sponsor.
• Any other Grade 4 toxicity.	Discontinue INCB050465 administration and follow-up per Protocol. Exceptions require approval of sponsor.

CMV = cytomegalovirus; IV = intravenous; PCR = polymerase chain reaction.

Table 4: Dose Levels and Reductions for INCB050465

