- ^f Required at baseline except for reasons provided in Section 7.6.2. If disease is present in bone marrow at baseline, a bone marrow biopsy is required to confirm CR.
- ^g PJP prophylaxis will continue for 2 to 6 months after the last dose of study treatment.
- ^h [REDACTED]
- ⁱ May be conducted by phone or email.

Table 7: Schedule of Laboratory Assessments

Laboratory Tests	Section	Screening	Treatment				EOT	Safety Follow-Up
		Day -28 to -1	Day 1	Every 4 Weeks Through Week 48 (± 3 Days)	Every 12 Weeks From Week 48 (± 1 Week)	Other		EOT + 30-35 Days
Serum chemistries	7.5.6.1	X	X ^a	X	X		X	X
Hematology ^b	7.5.6.1	X	X ^a	X	X	X ^c	X	X
Serology	7.5.6.3	X				X ^d	X	
Serum pregnancy	7.5.6.2	X ^e					X	X
Urine pregnancy	7.5.6.2					X ^f		
HIV testing	7.5.6.4	X ^g						
Tumor biopsy	7.8.5	X ¹				X ¹		

^a Day 1 assessments may be omitted if the screening tests occurred in the preceding 7 days. If needed, Day 1 blood draws should be performed before administration of study treatment.

^b Hematology samples will be collected every 2 weeks for the first 8 weeks.

^c Week 2 and Week 6 (± 3 days).

^d Samples for CMV DNA analysis only will be collected every 4 weeks from Day 1.

^e Only for females of childbearing potential; negative pregnancy test must be obtained within 14 days before administration of study treatment. May be performed by the central laboratory or the investigative site laboratory.

^f Only for females of childbearing potential. Must be conducted every 4 weeks from Day 1.

^g Optional for subjects enrolled in the United States.

¹ Subjects must be willing to undergo an incisional or excisional lymph node or tissue biopsy or provide a lymph node or tissue biopsy from the most recent available archival tissue. An optional biopsy should be collected at the time of progression if possible but may be collected at other times for safety or efficacy.

Table 8: Laboratory Tests: Required Analytes

Serum Chemistries	Hematology	Serology	Pregnancy Testing (Performed Locally)

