Description of change: Redefined “Grade 3 or Grade 4 ANC with an oral temperature of at least 38.5°C OR with Grade ≥ 3 infection” as Grade 3 or Grade 4 febrile neutropenia. Allowance is made to restart INCB050465 at the same dose after Grade 4 ANC, Grade 4 platelet count, or Grade 3 or Grade 4 febrile neutropenia resolve to \leq Grade 2, rather than Grade 1, regardless of attribution.

Rationale for change: A restart at the same dose level regardless of attribution is allowed to provide study doctors flexibility in subject management. Dosing is allowed to begin at \leq Grade 2 to be consistent with eligibility criteria, which start at Grade 2 for neutrophil and platelet counts.

3. Section 7.5.6, Laboratory Assessments

Description of change: Clarified the scenarios in which a local laboratory assessment may be performed and in which cases local laboratory values would be entered into the eCRF.

Rationale for change: Clarification.

4. Section 7.6.2, Bone Marrow Examination

Description of change: Clarified that bone marrow collected at screening and postbaseline should be sent to a local histopathology laboratory. [REDACTED]

Rationale for change: Clarification.

5. Section 3.1, Subject Inclusion Criteria (Inclusion Criterion 9d)

Description of change: Inclusion Criterion 9d was revised to allow subjects with whose total bilirubin values are $> 1.5 \times$ ULN to enroll if the elevation is due to Gilbert’s syndrome.

Rationale for change: Gilbert’s syndrome is a hereditary condition characterized by intermittent, unconjugated hyperbilirubinemia in the absence of hepatocellular damage and hemolysis. Consistent with other PI3K δ inhibitors, elevated bilirubin due to Gilbert’s syndrome is not expected to alter the risk/benefit profile for subjects taking INCB050465.

6. **Section 7.4, Prior and Concomitant Medications and Procedures**

Description of change: Added a definition for lines of therapy.

Rationale for change: Definitions were added to improve consistency for calculation of prior lines of therapy.

7. **Section 3.2, Subject Exclusion Criteria; Section 5.6.2, Restricted Medications; Section 5.6.3, Prohibited Medications and Therapies; Appendix B, Cytochrome P450 Inhibitors and Cytochrome P450 Inducers**

Description of change: Deleted Appendix B and references to Appendix B.

Rationale for change: Information was moved to the Pharmacy Manual.

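### Table 3 gives subjects enrolled with platelets > 100 × 10⁹/L an unconditional hold at Grade 2 and Grade 4 but only a conditional one for a count first seen at Grade 3 (25 to < 50)

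*Protocol*

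**What the plan says.** All platelet counts below are × 10⁹/L.

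Protocol Section 5.4.1.1, Table 3, has two hematology rows.

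- **First row.** For subjects enrolled above 100 the trigger begins "Platelet count is Grade 2 (50 to" and stops below 75. A separate trigger covers Grade 3 (below 50), but only for subjects enrolled at 100 or less. Treatment is held for up to 14 days until recovery to Grade 1 or better, or to the pre-treatment level. The restart rule is "Restart INCB050465 at same dose; monitor as clinically indicated".
- **Second row.** Grade 4 (below 25) is a trigger for everyone. The restart rule is "Restart INCB050465 at same dose. Monitor as clinically indicated. If recurs, start at next lower dose".

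Near the end of Table 3 a general row covers "Any Grade 3 toxicity, if clinically significant and not manageable by supportive care unless otherwise specified". Its restart is at the same dose, with this qualification: "If assessed as related to INCB050465, restart at next lower dose. If interrupted for > 14 days, contact the medical monitor".

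Section 5.4.1.1 also says that individual decisions rest on clinical judgment in consultation with the medical monitor. Section 5.4.1.3, on neutropenia and thrombocytopenia, tells sites what subjects should report and sets no platelet threshold.

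**The concern.** A dose-interruption rule should not relax as the toxicity worsens. For subjects who enter with the better counts, Table 3 holds at Grade 2, makes the hold conditional at Grade 3, and holds again at Grade 4. Subjects who enter with lower counts do have an unconditional hold at Grade 3, and the first hematology row also holds unconditionally for Grade 3 neutrophils. Nothing in the protocol explains why Grade 3 platelets are left out for one stratum.

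What is at stake is subject safety and consistent dosing across approximately 90 sites. If a site judges a first count of, say, 30 to be of no clinical consequence or manageable with supportive care, Table 3 asks for neither a hold nor a repeat count before the next scheduled one. The efficacy analysis is not at stake.

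**Working it through.** The plan gives no figure to reproduce here. The check sets the Table 3 triggers against each enrollment stratum and on-study count, taking the limits as printed.

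**Step 1. Which row applies as written**

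| On-study count | Grade | Enrolled > 100 | Enrolled ≤ 100 |
|---|---|---|---|
| 74, 60, 50 | 2 | First row: hold | No hematology row |
| 49, 40, 25 | 3 | **No hematology row; general Grade 3 row, conditional hold** | First row: hold |
| 24, 10 | 4 | Second row: hold | First and second rows: hold |

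In the > 100 stratum the sequence is hold, conditional, hold. The Grade 3 cell is the only one where a worse count has a weaker hold than a milder one.

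**Step 2. What differs once a subject is held**

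- *Recovery target.* The first row accepts Grade 1 or the pre-treatment level; the general row requires Grade 1. Since Grade 2 ends below 75, Grade 1 means 75 or more. A subject enrolled above 100 has a pre-treatment level above that, so the two targets amount to the same thing.
- *Restart dose.* The first row restarts at the same dose whatever the cause. The general row goes down one level when the event is attributed to the drug.

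Only the duty to hold is weaker at Grade 3. The restart after a related event is stricter.

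**Step 3. When the gap can occur**

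A subject seen at 60 is held until recovery, so a later fall to 30 happens during an existing hold. The gap needs a count first seen at 25 to < 50, for example after a fall from ≥ 75 to < 50 between samples. Table 7 footnote b states: "Hematology samples will be collected every 2 weeks for the first 8 weeks". The table's columns then give every 4 weeks through Week 48 and every 12 weeks after that. Intervals of 2, 4 and 12 weeks leave room for Grade 2 to be missed.

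**Step 4. Size**

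- Input: Protocol Section 1.3 reports new or worsening Grade ≥ 3 thrombocytopenia in 10% of 63 Phase 1/2 subjects with mixed B-cell malignancies.
- Assumption: the same rate applies here. Then 0.10 × 120 = 12 subjects.
- This is a ceiling under that assumption. It includes Grade 4, subjects enrolled at any count, and subjects who would already be held at Grade 2. The documents give none of the splits needed to subtract these, so the range under the assumption is 0 to about 12.

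**Step 5. After the change**

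With the > 100 trigger set at 25 to < 75, counts of 49, 40 and 25 fall in the first row and 24 and 10 stay in the second. No gap remains below 75 and no overlap is created. Written as < 75 with no lower limit, counts below 25 would match both rows, as they already do in the ≤ 100 stratum.

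**The case against.** The strongest reply is that this is a drafting omission in a guidance table. The authors probably meant Grade 2 or worse. Table 3 is titled as guidelines, Section 5.4.1 says treatment may be interrupted, and Section 5.4.1.1 leaves decisions to judgment with the medical monitor. Section 6.6 permits unscheduled visits. Sections 8.1.2 and 8.2 require adverse events, including qualifying laboratory abnormalities, to be followed, more often than at each visit if necessary. Section 5.5.1 requires stopping treatment for a related event judged not to be in the subject's interest. The Synopsis also describes visits with laboratory tests every 4 weeks after Week 8, so the 12-week interval rests on Table 7 alone.

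Most of this stands, and it limits the consequence. It does not close the gap. The discretion covers every row, so it cannot explain a weaker default at the worse grade, and the printed range ends at 50. If Grade 2 or worse was intended, the edit records that.

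Three stronger readings are tempting, and the documents do not support them:

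- *A subject at 60 is always held and a subject at 30 may always continue.* This fails for anyone already held at Grade 2, and it treats guidance as compulsion.
- *A confidence interval on the Phase 1 rate bounds the number affected.* Such an interval would describe all Grade ≥ 3 thrombocytopenia in another study. Its lower limit would say nothing about this cell, where the number could be zero.
- *The Grade 4 restart level is also an error, because a subject restarting at 50 to < 75 meets the first-row trigger.* Appendix F, Amendment 6, shows the rule was deliberate: "A restart at the same dose level regardless of attribution is allowed to provide study doctors flexibility in subject management", and recovery to Grade 2 was chosen "to be consistent with eligibility criteria, which start at Grade 2 for neutrophil and platelet counts". Read through its own steps, the Grade 4 row governs that recovery, so no change is needed there.

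**Conclusion.** The point holds in limited form. For subjects enrolled with platelets above 100, the hold guideline is unconditional at Grades 2 and 4 and conditional at Grade 3, and no other text found in the protocol repairs this. It matters for counts first detected at 25 to < 50.

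The conclusion rests on the printed limits of the Table 3 triggers and needs no numerical assumption. The ceiling of about 12 of 120 does need one: that the Phase 1/2 rate carries over to a different population and different schedules. The share of subjects enrolled above 100 and the rate of Grade 3 alone are not given.

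ORR, its confidence interval, the sample size and the futility rule do not change. This is a small safety and dosing-consistency correction, worth making because it is cheap.

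**What to change.** In the first hematology row of Table 3, change the platelet trigger for subjects enrolled above 100 × 10⁹/L to *Grade 2 or 3 (25 to < 75 × 10⁹/L)*. Keep the lower limit of 25 so that Grade 4 stays in its own row.

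Let that row's same-dose restart apply. It already applies to Grade 3 in subjects enrolled at ≤ 100, and the Grade 4 row does the same for a first event. If the sponsor prefers to keep a step down for related events at 25 to < 50, the row should say so.

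**Cost.** One trigger edit in the next amendment, with no new procedures. A few Grade 3 events now managed without interruption would be held for up to 14 days. Under Section 5.5.1 a delay beyond 14 days for a persistent event means discontinuation unless the sponsor approves it.

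The restart choice has a price either way:

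- The same-dose restart gives up the reduction that the general row now applies to related events.
- Keeping that reduction would extend it to newly held events. In Group B maintenance this means going from 2.5 to 1 mg QD, and Table 4 has no second reduction level there. It would also leave a related Grade 3 event with a stricter restart than a first Grade 4 event.

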Timepoint	Dose (Group A)	Dose (Group B)
Starting dose	20 mg QD for 8 weeks (Day 1 through Day 56)	20 mg QD for 8 weeks (Day 1 through Day 56)
First dose reduction	10 mg QD	10 mg QD
Second dose reduction	5 mg QD	5 mg QD
Week 9 (Day 57) onward	20 mg once weekly ^a	2.5 mg QD ^b
First dose reduction	10 mg once weekly	1 mg QD ^c
Second dose reduction	5 mg once weekly	NA

^a All subjects will receive 20 mg once weekly at Week 9 (Day 57) regardless of prior dose level, unless a dose modification of a switch to a QW schedule before Week 9 is required for diarrhea/colitis management (see [Table 5](#)).

^b All subjects will receive 2.5 mg QD at Week 9 (Day 57) regardless of prior dose level, unless a dose modification of a switch to a QW schedule is required for diarrhea/colitis management (see [Table 5](#)).

^c Further dose modification due to diarrhea or colitis for subjects on 1 mg QD is permitted (see [Table 5](#)).

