#### **Amendment 1 (26 AUG 2020)**

- Section 3 was modified to increase the target enrollment from approximately 100 to approximately 120 participants. This change is to align with recommendations from FDA.
- Section 4.1.4 was updated to include details of rules for handling partial/missing onset or end date of TEAEs in the calculation of time to onset or duration of a TEAE. Rules for partial/missing date of last dose were updated to include details for when both month and day are missing.
- Section 5.2 was modified to provide details regarding how crossover participants will be summarized.
- Section 5.3 was updated to add the all-screened population for the summary of analysis populations.
- Section 6.1.2 was updated to add relapsed/refractory status to the most recent prior therapy to the summary table of disease history because the response to last regimen before entering the study may be a prognostic factor for clinical outcomes.
- Section 6.2 was modified to add summaries of participants who are ongoing with treatment or still in the study.
- Section 6.4 was modified to change the calculations of duration of treatment and average dose during the maintenance dosing period because Group B with 2.5 mg QD was selected as the maintenance dose.
- Section 7.3 was updated to change the timing of the primary analysis to align with recommendations from FDA.
- Section 7.3.2 was modified to add "unknown" as a category for bone marrow involvement at baseline. Relapsed/refractory status to the most recent prior therapy was added to the subgroup analysis because the response to last regimen before entering the study may be a prognostic factor for clinical outcomes.
- Section 7.4.3 was modified to update references of censoring for PFS.

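### Protocol Tables 3 and 4 do not fit together for Group B from Week 9: Table 4 lists one dose reduction, but Table 3's stopping row for recurrent Grade 3 toxicity asks for two

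*Protocol*

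**What the plan says.** The rules sit in three linked protocol tables (Sections 5.4.1.1 and 5.4.1.2).

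- **Table 3, stopping row.** For "Any recurrent Grade 3 toxicity after 2 dose reductions" the action is "Discontinue INCB050465 administration and follow-up per Protocol. Exceptions require approval of sponsor". The row names neither a treatment group nor a dosing period, and does not say how reductions are counted.
- **Table 4, Weeks 1 to 8 (the lead-in).** Both groups start at 20 mg QD. The first reduction is 10 mg QD, and the next line reads "Second dose reduction 5 mg QD 5 mg QD" (Group A, then Group B).
- **Table 4, Week 9 onward.** The first reduction line reads "First dose reduction 10 mg once weekly 1 mg QD" and the second "Second dose reduction 5 mg once weekly NA", in the same column order.
- **Table 4, footnote b (Group B).** "All subjects will receive 2.5 mg QD at Week 9 (Day 57) regardless of prior dose level", unless diarrhea or colitis requires a weekly schedule.
- **Table 4, footnote c (attached to 1 mg QD).** "Further dose modification due to diarrhea or colitis for subjects on 1 mg QD is permitted", with a reference to Table 5.

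SAP Section 11.2 (Amendment 1) shows which regimen was chosen. The maintenance exposure calculations were changed "because Group B with 2.5 mg QD was selected as the maintenance dose".

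**The concern.** Table 3 makes the stopping row depend on two reductions, and the selected maintenance regimen lists only one. A site with a subject on 1 mg QD and a recurrent, related Grade 3 event finds two instructions. One sends the subject down a level that Table 4 does not list. The other stops treatment only after a count that the subject may not have reached. The tables do not say which prevails.

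The gap falls where such events may be expected. Protocol Section 5.4.1.4 says that most immune-related events in Study INCB 50465-101 came after the first 9 weeks. Section 1.3 reports 12 of 63 subjects in that study stopping for adverse events, with all but one of the events after the 9-week assessment (12 − 1 = 11). Those subjects had daily or daily-then-weekly dosing, so this shows timing only and gives no rate for Group B maintenance.

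At stake are clear safety instructions and consistent handling across about 90 sites. The SAP counts reductions per participant (Section 6.4) and tabulates events leading to reduction or discontinuation (Section 9.2.3). Uneven handling could therefore reach the reported safety tables.

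**Working it through.** The plan states no figure on this point. The check counts the levels in Table 4 and sets them against Table 3.

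**1. Reductions listed in Table 4**

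| | Weeks 1–8 | Week 9 onward | Total |
|---|---|---|---|
| Group A | 2 (10, 5 mg QD) | 2 (10, 5 mg once weekly) | 2 + 2 = 4 |
| Group B | 2 (10, 5 mg QD) | 1 (1 mg QD) | 2 + 1 = 3 |

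**2. Stopping row for a Group B subject on 1 mg QD (outside diarrhea/colitis)**

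The row needs a count of 2. The protocol does not say whether the count carries across Week 9 or restarts there, so both readings are shown.

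| Lead-in reductions | Count if carried over | Count if restarted |
|---|---|---|
| 0 | 0 + 1 = 1 | 1 |
| 1 | 1 + 1 = 2 | 1 |
| 2 | 2 + 1 = 3 | 1 |

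With no lead-in reduction, the subject falls short under either reading. With one or two, the answer depends on the unstated counting rule. Within Weeks 1 to 8, both groups can reach 2. In Group A maintenance, 2 can be reached from the listed levels alone.

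**3. Other Table 3 rows that call for a lower dose**

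These are:
- Grade 3 ALT/AST
- recurrence of Grade 4 ANC, Grade 4 platelets or febrile neutropenia
- Grade 1 pneumonitis
- Grade 1 exfoliative dermatitis
- skin toxicity judged related
- CMV infection, where treatment is restarted after an interruption
- clinically significant Grade 3 events judged related

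For a subject on 1 mg QD, Table 4 lists no lower level. The same is true at 5 mg once weekly in Group A and at 5 mg QD in the lead-in.

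**4. Diarrhea and colitis**

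Footnote c points from 1 mg QD to Table 5. There, the row for Grade 3 or higher diarrhea and noninfectious colitis works: any daily dose moves to a weekly schedule, and that schedule has a stated end. Recurrent Grade 2 diarrhea is routed to the same row. For Grade 2 diarrhea that needed steroids, however, Step 4 calls for one level down and refers to Table 4, where the entry after 1 mg QD is NA. That reference is circular.

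**5. Size**

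Planned Group B allocation is 50/2 + 70 = 25 + 70 = 95 of 120. Some of the 25 Group A subjects may also switch in. The gap needs more than allocation: a reduction to 1 mg QD, then a further qualifying event and, for the stopping row, no lead-in reduction that counts. The documents give no frequency for this.

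**The case against.** The strongest reply is that the stopping row carries no limit by period. On its plain words, two lead-in reductions satisfy it, and so does one lead-in reduction plus the step to 1 mg QD. Footnote b resets the dose and says nothing about resetting the count. This stands. A reader might infer that the row can never be met in the selected regimen; the documents do not support that, because the regimen includes the first 8 weeks.

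Second, other protections exist. Section 5.5.1 requires discontinuation if the subject cannot tolerate treatment, if a related event is judged against the subject's interest, or if an event delays dosing beyond 14 days without sponsor approval. Section 5.4.1.1 asks for dose decisions in consultation with the medical monitor, and the ALT/AST and CMV rows require the monitor's approval to restart. A reader might infer that affected subjects have no stopping criterion, or that sites are left entirely to improvise; neither follows. These are judgment-based routes, though, and do not settle what the tables mean.

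Third, NA might be taken to mean stop. The protocol does not say so at 1 mg QD, whereas Table 5 states permanent discontinuation explicitly at the bottom of the weekly schedule.

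Fourth, a reader might take 95 of 120 as the number affected, or Group A as untouched. The first is only the planned allocation. The second holds for reaching the stopping row in maintenance, but not for the missing lower dose.

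**Conclusion.** The point holds in a bounded form. From Week 9, outside the diarrhea/colitis route, a Group B subject with no lead-in reduction cannot meet Table 3's two-reduction row through the levels that Table 4 lists. Several other Table 3 rows, and Step 4 for Grade 2 diarrhea in Table 5, direct a subject on 1 mg QD to a level that is not there. For subjects with a lead-in reduction, the outcome turns on a counting rule that the protocol omits. The missing lower level also exists at the lowest listed dose in Group A maintenance and in the lead-in.

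This rests on reading NA as no further level listed, and on treating the Week 9 change as the scheduled dose and not as a reduction. The number of subjects concerned is below the planned 95 and cannot be derived from the documents. ORR, the sample size and the futility rule are not affected. The correction should be made because two stated safety rules do not work together in the selected regimen.

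**What to change.** Reconcile Tables 3, 4 and 5 for a subject already on the lowest listed dose, in particular Group B from Week 9. The text should state:

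1. what applies at 1 mg QD when a Table 3 row calls for a lower dose, and likewise at 5 mg once weekly and at 5 mg QD in the lead-in;
2. how the stopping row for recurrent Grade 3 toxicity operates where only one reduction is listed;
3. whether lead-in reductions count toward the two;
4. what Step 4 for Grade 2 diarrhea means at 1 mg QD.

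The clinical content is for the sponsor to decide; no dose or rule is proposed here. The cost is wording in the tables, by protocol amendment or clarification letter, with no change to the efficacy analyses.
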